8.5.3 E-mail: [contact] Reporting Pregnancy to Amgen

If a subject or spouse or partner of a subject becomes pregnant while enrolled in this clinical trial or up to three months following administration of carfilzomib, Amgen Drug Safety must be notified within 24 hours of the Investigator, designee, or site personnel learning of the pregnancy (See Amgen Drug Safety and Pharmacovigilance Contact information above). If the subject is pregnant, carfilzomib must be withheld.

Subjects, spouses, or partners will be followed through the outcome of the pregnancy. The Investigator will be required to report the results to Amgen Drug Safety.

If the outcome of the pregnancy meets a criterion for immediate classification as an SAE—spontaneous abortion (any congenital anomaly detected in an aborted fetus is to be documented), stillbirth, neonatal death, or congenital anomaly—the Investigator should repeat the procedures for expedited reporting of SAEs as outlined above.

8.5.4 Reporting Pregnancy to Celgene

Pregnancy of a female subject or the female partner of a male subject occurring while the subject is on lenalidomide or within 4 weeks after the subject's last dose of lenalidomide are considered expedited reportable events. If the subject is on lenalidomide, it is to be discontinued immediately and the subject is to be instructed to return any unused portion of lenalidomide to the Investigator. The pregnancy must be reported to Celgene Drug Safety within 24 hours of the Investigator's knowledge of the pregnancy by phone and facsimile using the SAE Form.

The Investigator will follow the pregnant female until completion of the pregnancy, and must notify Celgene Drug Safety of the outcome as specified below. The Investigator will provide this information as a follow-up to the initial SAE.

If the outcome of the pregnancy meets the criteria for immediate classification as a SAE (i.e., spontaneous abortion [any congenital anomaly detected in an aborted fetus is to be documented], stillbirth, neonatal death, or congenital anomaly), the Investigator should follow the procedures for Expedited Reporting of SAEs to Celgene (i.e., report the event to Celgene Drug Safety by facsimile within 24 hours of the Investigator's knowledge of the event).

Any suspected fetal exposure to lenalidomide must be reported to Celgene within 24 hours of

being made aware of the event. The pregnant female should be referred to an obstetrician/gynecologist experienced in reproductive toxicity for further evaluation and counseling.

All neonatal deaths that occur within 30 days of birth should be reported, without regard to causality, as SAEs. In addition, any infant death after 30 days that the Investigator suspects is related to the *in utero* exposure to lenalidomide should also be reported.

In the case of a live “normal” birth, Celgene Drug Safety should be advised as soon as the information is available

8.6 REPORTING PREGNANCY TO CCR

8.6.1 Maternal exposure

If a patient becomes pregnant during the course of the study, the study treatment should be discontinued immediately, and the pregnancy reported to the Sponsor no later than 24 hours of when the Investigator becomes aware of it. The Investigator should notify the Sponsor no later than 24 hours of when the outcome of the Pregnancy becomes known,

Pregnancy itself is not regarded as an SAE. However, congenital abnormalities or birth defects and spontaneous miscarriages that meet serious criteria (section 8.1.2) should be reported as SAEs.

The outcome of all pregnancies (spontaneous miscarriage, elective termination, ectopic pregnancy, normal birth, or congenital abnormality) should be followed up and documented.

8.6.2 Paternal exposure

Male patients should refrain from fathering a child or donating sperm during the study and for 28 days after the last dose of study therapy.

Pregnancy of the patient’s partner is not considered to be an AE. However, the outcome of all pregnancies (spontaneous miscarriage, elective termination, ectopic pregnancy, normal birth, or congenital abnormality) occurring from the date of the first dose until 28 days after the last dose should, if possible, be followed up and documented.

8.7 REGULATORY REPORTING FOR STUDIES CONDUCTED UNDER CCR-SPONSORED IND

Following notification from the investigator, CCR, the IND sponsor, will report any suspected adverse reaction that is both serious and unexpected. CCR will report an AE as a suspected adverse reaction only if there is evidence to suggest a causal relationship between the study product and the adverse event. CCR will notify FDA and all participating investigators (i.e., all investigators to whom the sponsor is providing drug under its INDs or under any investigator’s IND) in an IND safety report of potential serious risks from clinical trials or any other source, as soon as possible, in accordance to 21 CFR Part 312.32.

All serious events will be reported to the FDA at least annually in a summary format.

8.8 SPONSOR PROTOCOL NON-ADHERENCE REPORTING

Protocol non-adherence is defined as any noncompliance with the clinical trial protocol, GCP, or protocol-specific procedural requirements on the part of the participant, the Investigator, or the

study site staff inclusive of site personnel performing procedures or providing services in support of the clinical trial.

It is the responsibility of the study Staff to document any protocol non-adherence identified by the Staff or the site Monitor on the OSRO Site Protocol Non-Adherence Log. The protocol-specific, cumulative non-adherence log should be maintained in the site essential documents file and submitted to OSRO via [contact] on the **first business day of each month over the duration of the study**. In addition, any non-adherence to the protocol should be documented in the participant's source records and reported to the local IRB per their guidelines. OSRO required protocol non-adherence reporting is consistent with E6(R2) GCP: Integrated Addendum to ICH E6(R1): 4.5 Compliance with Protocol; 5.18.3 (a), and 5.20 Noncompliance; and ICH E3 16.2.2 Protocol deviations.

9 CLINICAL MONITORING

As a sponsor for clinical trials, FDA regulations require the CCR to maintain a monitoring program. The CCR's program allows for confirmation of: study data, specifically data that could affect the interpretation of primary study endpoints; adherence to the protocol, regulations, and SOPs; and human subjects protection. This is done through independent verification of study data with source documentation focusing on:

- Informed consent process
- Eligibility confirmation
- Drug administration and accountability
- Adverse events monitoring
- Response assessment.

The monitoring program also extends to multi-site research when the CCR is the coordinating center.

This trial will be monitored by personnel employed by an CCR contractor. Monitors are qualified by training and experience to monitor the progress of clinical trials. Personnel monitoring this study will not be affiliated in any way with the trial conduct.

10 STATISTICAL CONSIDERATIONS

10.1 STUDY DESIGN/PRIMARY ENDPOINTS

This is a single arm phase II study designed to evaluate efficacy of combinational therapy of carfilzomib, dexamethasone, and lenalidomide in newly diagnosed untreated MM patients. The primary objectives of this study are to determine if the combination of carfilzomib, lenalidomide and dexamethasone has acceptable toxicity in patients with newly diagnosed MM.

10.2 SAMPLE SIZE DETERMINATION

The sample size on which the trial will be based will be that necessary to demonstrate if the rate of grade 3 or worse neurologic toxicity is lower than 10%, or if it could be consistent with a rate which is greater than 10%, in which case it would be considered excessive.

We will plan to enroll a total of 45 evaluable patients in a single cohort and score each patient for the development of grade 3 or worse neurologic toxicity in the first two completed cycles of treatment. If we enroll 45 patients and if 5 or more have grade 3 or worse neurologic toxicity,

then the probability that the true rate of grade 3+ neurologic toxicity is 5% is 7.3% while the probability that the true rate of grade 3+ neurologic toxicity is 15% is 82.5%. Thus, the appearance of 5 or more patients with grade 3+ neurologic toxicity in 45 patients will provide evidence that the true rate of toxicity is consistent with 15%, and will be considered excessive.

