1.2.8 Proposed Study Investigation with Correlative Studies

Given carfilzomib's potent anti-myeloma activity and lack of peripheral neuropathy, we propose a phase II investigation of combination therapy (Cycles 1-8 carfilzomib, lenalidomide, dexamethasone) in newly diagnosed MM patients followed by extended dosing with lenalidomide (days 1-21 of 28 day cycle) for 12 cycles. Patients will be enrolled on study to determine if the CRd 3 drug-combination demonstrates a rate of grade 3 or worse neurologic toxicity lower than 10% in the first two completed cycles. After 4 cycles, transplant eligible patients will undergo autologous stem cell harvesting. After 8 cycles, patients achieving SD or better will proceed to extended dosing with lenalidomide. Patients not achieving SD will be off treatment. Response criteria is outlined in Section 5.3. Proposed correlative studies include gene expression profiling on purified CD 138 + pre- and post- carfilzomib plasma cells, identification of potential biomarkers (blood, urine, bone marrow aspirates), proteasome quantification and activity, ubiquitination assays, and effects on downstream signaling targets. Patients will also undergo evaluation for minimal residual disease at regular interval time points, using multi-parametric flow cytometry, FDG PET-CT, and detection of clonality using heavy and/or light chain immunoglobulin rearrangement. Effective with Amendment L (version date 07/15/2015), bone marrow aspirate and biopsy will be obtained for research studies at the discretion of the PI.

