3.1 STUDY DESIGN

- Patients with newly diagnosed MM will be enrolled on the Phase II study and treated with 3 drug combination (Cycles 1-8 carfilzomib, lenalidomide, dexamethasone) followed by extended lenalidomide dosing.
- After receiving first 4 cycles, patients who are considered to be eligible for subsequent high dose therapy/autologous stem cell transplant (ASCT) will undergo autologous stem cell harvesting for potential use in the future. In accord with current clinical standards, the decision whether a given patient is eligible for subsequent high dose therapy/ASCT, or not, will be based on a clinical assessment conducted by the transplant center that evaluates the patient.
- For patients who choose to undergo stem cell harvest, next cycle may be delayed for up to 5 weeks.
- After 8 cycles, patients achieving SD or better will proceed to extended dosing phase I of lenalidomide (Days 1-21 of 28 day cycle) for 12 cycles. After 12 cycles of extended dosing of lenalidomide, patients who maintain their current clinical response and do not meet criteria of PD as defined in Section 6.3 will have the option to continue lenalidomide as clinically indicated for an additional year on extended dosing phase II.
- Patients not achieving SD will be off treatment.
- Patients will be enrolled on study to determine if the CRd 3 drug-combination demonstrates a rate of grade 3 or worse neurologic toxicity of 10% or lower in the first two completed cycles. A rate greater than 10% will be considered excessive.

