10.3 STATISTICAL ANALYSES

10.3.1 Analysis of the Primary Endpoints

The 90% and 95% confidence intervals will be constructed around the observed fraction of patients with grade 3+ neurologic toxicity, and will be reported along with the observed incidence. If 5/45 are noted to have grade 3+ neurologic toxicity, the exact two-sided 90% CI bound extends from 4.5% to 22.0%, thus confirming that this rate of toxicity is likely to exceed 5%, and is consistent with as high as 22%.

As an early stopping rule for toxicity for the first 20 patients: if 4 patients are found to have grade 3+ neurologic toxicity in the first two completed cycles of treatment, no further patients will be enrolled. As soon as this can be determined, since the lower 80% one-sided confidence bound around 4/20 is 11.7%, which, being greater than 10%, would be considered demonstration of excessive toxicity. In fact, the lower 80% bounds range from 67% for observing 4 patients with grade 3+ neurologic toxicity in the first 4 patients to 12% for observing 4 patients with grade 3+ neurologic toxicity in 20 patients.

The rates of VGPR+CR and CR alone will also be estimated and reported. These rates are expected to be fairly high. Two-sided 95% confidence interval bounds will be formed around each of these measures.

In order to allow for a small number of inevaluable patients, the accrual ceiling will be set at 50.

It is anticipated that 2-3 patients per month may enroll on this trial; thus, 2 years is anticipated as the accrual period for this study.

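### Section 10.2 presents 45 patients as enough to show whether grade 3+ neurologic toxicity is below 10%, but the final rule separates 5% from 15%, and 4 or fewer events does not in general show a rate below 10%

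*Combined protocol and SAP*

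**What the plan says.** Section 10.2 states the purpose of the sample size: it "will be that necessary to demonstrate if the rate of grade 3 or worse neurologic toxicity is lower than 10" per cent, or could be consistent with a rate above 10%, which would be excessive. The plan is then: "We will plan to enroll a total of 45 evaluable patients in a single cohort". Each patient is scored over the first two completed cycles. Five or more events in 45 "will provide evidence that the true rate of toxicity is consistent with 15%, and will be considered excessive". The only true rates at which Section 10.2 describes this rule are 5% (7.3%) and 15% (82.5%).

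Section 1.2.8 says patients are enrolled to determine whether the combination "demonstrates a rate of grade 3 or worse neurologic toxicity lower than 10% in the first two completed cycles". Section 3.1 differs slightly: whether it "demonstrates a rate of grade 3 or worse neurologic toxicity of 10% or lower in the first two completed cycles", followed by "A rate greater than 10% will be considered excessive".

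Section 10.3.1 sets the reporting: "The 90% and 95% confidence intervals will be constructed around the observed fraction of patients with grade 3+ neurologic toxicity". Its example is the exact two-sided 90% interval for 5/45, 4.5% to 22.0%. The same section bases early stopping at 4 of the first 20 on a different bound: "since the lower 80% one-sided confidence bound around 4/20 is 11.7%, which, being greater than 10%, would be considered demonstration of excessive toxicity".

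No section gives a count, limit or confidence level at which the rate would be regarded as lower than 10%, and none says what 0 to 4 events in 45 would mean.

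**The concern.** The 10% figure appears in the stated purpose but does not enter the final rule. A reader of Sections 10.2, 1.2.8 and 3.1 would expect that a trial with fewer than 5 events has shown a rate below 10%. The rule was not built to support that conclusion: its cutoff lies between 5% and 15%, and a result just under the cutoff is compatible with rates well above 10%.

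This is the primary endpoint. With 1 to 4 events, the trial could be reported as meeting its below-10% aim while the interval printed beside the estimate extends past 10%, in the worst case to about 20%.

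**Working it through.** **Inputs.** n = 45 evaluable and cutoff 5 (Section 10.2); true rates 5% and 15% (10.2) and 10% (10.2, 1.2.8, 3.1); 90% and 95% intervals, with the exact method shown for the 90% example (10.3.1); one-sided 80% level from the early stopping rule (10.3.1). Applying the exact method to the 95% interval is an assumption.

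**Step 1. Reproduce the plan's figures.** The flag probability is P(X ≥ 5) = 1 − Σ C(45,k) p^k (1−p)^(45−k), summed over k = 0 to 4.
- p = 5%: 1 − (0.0994 + 0.2355 + 0.2727 + 0.2057 + 0.1137) = 1 − 0.9271 = 0.0729. Printed: 7.3%.
- p = 15%: 0.8252. Printed: 82.5%.
- Exact 90% interval for 5/45: 4.48% to 21.95%. Printed: 4.5% to 22.0%.
- One-sided 80% lower bound for 4/20: 11.70%. Printed: 11.7%.

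All agree. Section 10.2 words the first two as probabilities that the true rate is 5% or 15%; they reproduce as probabilities of 5 or more events given those rates, and are read that way here.

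**Step 2. The same rule at 10%.** P(X ≥ 5) = 1 − (0.0087 + 0.0436 + 0.1067 + 0.1699 + 0.1982) = 1 − 0.5271 = 0.4729. At a true rate of exactly 10%, the trial ends with 4 or fewer events 52.7% of the time.

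**Step 3. What each non-excessive count can exclude.** The exact upper limit at x events is the rate p that solves P(X ≤ x | 45, p) = a, with a = 0.05 for the 90% interval, 0.025 for the 95% interval and 0.20 for a one-sided 80% bound. For x = 0 this is 1 − a^(1/45); for example 1 − 0.05^(1/45) = 1 − 0.9356 = 6.4%.

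| Events in 45 | 90% upper limit | 95% upper limit | One-sided 80% upper bound |
|---|---|---|---|
| 0 | 6.4% | 7.9% | 3.5% |
| 1 | 10.1% | 11.8% | 6.5% |
| 2 | 13.3% | 15.1% | 9.3% |
| 3 | 16.3% | 18.3% | 11.9% |
| 4 | 19.2% | 21.2% | 14.5% |

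On the planned exact intervals, only 0/45 is below 10%. On the one-sided 80% bound, 0 to 2 events are. At 3 and 4 events none of the three is.

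**Step 4. How firm the 1-event row is.** At n = 45 the exact 90% limit is 10.11%, a miss of 0.11 points. With 46 evaluable it is 9.9%; with all 50 of the accrual ceiling evaluable it is 9.1%. At 1/45, other 90% limits fall below 10%: Wilson 9.4%, mid-P 8.8%, Jeffreys 8.4%. At 95%, 1/45 still includes 10% by the exact (11.8%), Wilson (11.6%) and mid-P (10.5%) methods; Jeffreys (9.9%) just excludes it.

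**Step 5. How often this would arise at the favourable design rate.** At a true rate of 5%: P(0) = 0.95^45 = 9.9%; P(0 to 2) = 0.0994 + 0.2355 + 0.2727 = 60.8%; P(0 to 4) = 92.7%.
- By the exact 90% or 95% limit, a non-excessive result that does not exclude 10% has probability 92.7% − 9.9% = 82.8%.
- By the one-sided 80% bound it has probability 92.7% − 60.8% = 31.9%.

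At lower true rates zero events is more likely: P(0) is 25.4%, 40.3% and 63.6% at 3%, 2% and 1%.

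**The case against.** The strongest defence is that the sentence in Section 10.2 has two branches: whether the rate is lower than 10%, or whether it could be consistent with more. That can be read as sorting results into acceptable and excessive, with no promise of an upper bound below 10%. A cutoff of 5/45 (11.1% observed), set between 5% and 15%, is a conventional way to put a 10% boundary into practice, and the rates, cutoff and tail probabilities are all printed. This stands in part. The second branch is met at 5/45, whose 90% interval reaches 22.0%. But 4/45 is also consistent with a rate above 10% and is not called excessive, so even as a sorting rule the 10% wording does not describe what the cutoff does.

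Three stronger readings are tempting, and the documents do not support them.

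- A reader might infer that a rate below 10% can be shown only with zero events. The plan never makes the 90% or 95% upper limit the test; Section 10.3.1 has those intervals for reporting. The one place where it speaks of demonstration is the interim rule, at a one-sided 80% level, and at that level 0 to 2 events would qualify. The plan does not set that level for an upper bound in the 45 patients either, so the criterion is open. The zero-events statement holds only for the exact intervals at n = 45.
- A reader might take the 47.3% flag rate at 10% for an error. A flag rate near one half is expected at the midpoint of a rule that separates 5% from 15%.
- A reader might infer that the interim and final rules contradict each other, since the one-sided 80% lower bound is 11.7% at 4/20 but only 6.9% at 5/45. Both bases are printed, and a stopping rule and a final evaluation may use different references. This needs no change.

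It is also true that both intervals are reported at any count, so a reader would see the upper limit. That limits the harm, but leaves the reported interval at odds with the stated purpose.

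**Conclusion.** The concern holds as a mismatch between the stated purpose and the operating characteristics. The plan's arithmetic is correct. With n = 45 and a cutoff of 5, the design separates 5% from 15%, and 4 or fewer events does not in general demonstrate a rate below 10%. At 3 or 4 events no level considered here excludes 10%. At 1 or 2 events the answer depends on a criterion that the plan does not give, and at 1 event also on the method and the number evaluable. At 0 events 10% is excluded at every level considered.

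This rests on independent binomial outcomes, 45 evaluable patients and exact limits. It should be fixed because it governs what may be concluded on the primary endpoint, but it is a matter of wording and interpretation, not of enrolment.

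**What to change.** In Section 10.2, replace the purpose sentence and add the missing interpretation, for example:

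> The sample size of 45 and the cutoff of 5 are chosen to separate a grade 3+ neurologic toxicity rate of 5% from 15%. The probability of 5 or more events is 7.3%, 47.3% and 82.5% if the true rate is 5%, 10% and 15%. Four or fewer events means that toxicity was not shown to be excessive. A rate below 10% will be claimed only if the upper limit of the exact 90% interval planned in Section 10.3.1, computed for the actual number evaluable, is below 10% (with 45 patients, only at 0 events).

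Naming the exact 90% interval is a choice; what matters is that one method and level are fixed. Align Sections 1.2.8 and 3.1 with this text, which also removes the difference between lower than 10% and 10% or lower.

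Section 1.2.10 already reports no grade 3 or higher neuropathy in the first 20 patients, so the change should be dated as made after those data were known.

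The cost is an amendment to wording in three sections. The sample size, cutoff, early stopping rule and Section 10.3.1 do not change. The downside is a less favourable conclusion after 1 to 4 events: not shown to be excessive, without a claim of a rate below 10% unless the stated limit supports it.

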- Patients achieving stable disease or better after 8 cycles of CRd will receive lenalidomide extended dosing (phase I) for 12 cycles. After 12 cycles, patients will have the option to continue extended dosing (phase II) for one additional year.
- Patients will have routine blood work with SPEP and free light chains monthly during the induction phase. Laboratory evaluations may be spread out to every 3 months during the

maintenance and follow-up phases.

- Pre- and post-treatment in addition to follow-up bone marrow biopsies will be obtained for confirmation of diagnosis, response and durability, and correlative studies.
- Patients will also undergo evaluation for minimal residual disease at regular interval time points, using multi-parametric flow cytometry and FDG PET-CT.
- A single stage phase II design will be employed, with an early stopping rule. Unless 4 or more patients in the first 20 have Grade 3 or higher neurologic toxicity in the first 2 completed cycles, a total of 45 evaluable patients will be enrolled in this study.

TABLE OF CONTENTS

PRÉCIS	2
TABLE OF CONTENTS.....	4
1 INTRODUCTION.....	7
1.1 Study Objectives.....	7
1.2 Background and Rationale	7
2 ELIGIBILITY ASSESSMENT AND ENROLLMENT	14
2.1 Eligibility Criteria.....	14
2.2 Screening Evaluation	16
2.3 Registration Procedures	16
2.4 Baseline Evaluation	17
3 STUDY IMPLEMENTATION	18
3.1 Study Design	18
3.2 Drug Administration	19
3.3 Dose Modifications.....	22
3.4 Study Calendar.....	28
3.5 Criteria for Removal from Protocol Therapy and Off Study Criteria	31
4 CONCOMITANT MEDICATIONS/MEASURES.....	31
4.1 Tumor lysis syndrome.....	31
4.2 Bone Disease/Extramedullary Disease.....	32
4.3 Hypercalcemia.....	33
4.4 Transfusions/Growth Factors.....	33
4.5 Anti-Coagulation.....	33
4.6 HSV, VSV Prophylaxis.....	33
5 BIOSPECIMEN COLLECTION	34
5.1 Correlative Samples for Research/Pharmacokinetic Studies.....	34
5.2 Sample Storage, Tracking and Disposition.....	41
5.3 Samples for Genetic/Genomic Analysis.....	43
6 DATA COLLECTION AND EVALUATION.....	43
6.1 Data Collection.....	43
6.2 Data Sharing Plans.....	45
6.3 Response Criteria.....	45
6.4 Toxicity Criteria.....	47

7	NIH REPORTING REQUIREMENTS/DATA AND SAFETY MONITORING PLAN ..	48
7.1	Definitions.....	48
7.2	OHSRP Office of Compliance and Training / IRB Reporting	48
7.3	NCI Clinical Director Reporting.....	48
7.4	NIH Required Data and Safety Monitoring Plan.....	48
8	SPONSOR PROTOCOL/SAFETY REPORTING	49
8.1	Definitions.....	49

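### Section 10.2's 7.3% and 82.5% leave out the 4-in-20 stop and are worded as probabilities of the true rate; with both rules they are 7.7% and 82.8%

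*Combined protocol and SAP*

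**What the plan says.** The plan has two routes to a conclusion of excessive toxicity.

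- **Final rule (10.2).** The sample is fixed by the sentence "We will plan to enroll a total of 45 evaluable patients in a single cohort". The rule is that "the appearance of 5 or more patients with grade 3+ neurologic toxicity in 45 patients" will be taken as excessive.
- **Early rule (10.3.1).** Applied to an initial group of 20, it reads: "if 4 patients are found to have grade 3+ neurologic toxicity in the first two completed cycles of treatment, no further patients will be enrolled". The section justifies this by a one-sided 80% lower bound of 11.7% for 4/20. Because that bound lies above 10%, it treats the stop as showing excessive toxicity. The Précis states the same rule: "Unless 4 or more patients in the first 20 have Grade 3 or higher neurologic toxicity in the first 2 completed cycles", 45 evaluable patients will be enrolled.

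Probabilities are attached only to the final rule. Section 10.2 opens with "If we enroll 45 patients and if 5 or more have grade 3 or worse neurologic toxicity" and continues "then the probability that the true rate of grade 3+ neurologic toxicity is 5% is 7.3" per cent, "while the probability that the true rate of grade 3+ neurologic toxicity is 15% is 82.5" per cent. It does not mention the early stop, and neither document section gives probabilities for the two rules taken together.

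**The concern.** These two figures are the only decision probabilities the plan gives for its primary endpoint. A reader will take 7.3% as the chance of wrongly calling a 5% regimen too toxic, and 82.5% as the chance of catching a 15% regimen.

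Two things stand in the way of that reading. First, a trial that stops with 4 events in its first 20 patients is declared too toxic even if the next 25 would all have been event-free. A calculation that always enrols 45 counts that outcome as acceptable, so it must give a probability that is somewhat too low. Second, the sentence turns the conditional round. It speaks of the probability that the true rate has a given value once 5 events are seen. A binomial calculation cannot give that without a prior on the rate, and the plan states none.

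What is at stake is the accuracy of the stated operating characteristics and how they are carried into a report, not the conduct of the trial.

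**Working it through.** **Inputs.** n = 45 and cutoff 5 (10.2); early stop at 4 events in the first 20 (10.3.1 and Précis); true rates p = 5% and 15% (10.2). Write X20 for events in the first 20 patients and X25 for events in the next 25. Outcomes are taken as independent with a common p.

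**Step 1. Reproduce the plan's figures.** Fixed sample, P(X ≥ 5) for X ~ Binomial(45, p):

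- p = 0.05: 0.0729, which rounds to the stated 7.3%.
- p = 0.15: 0.8252, which rounds to the stated 82.5%.

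Neighbouring cutoffs do not match: 4 or more gives 18.7% and 92.2%, and 6 or more gives 2.4% and 68.6%. So the stated numbers are P(5 or more events given the rate), at fixed n = 45 with no early stop. This also shows that they are not probabilities of the rate.

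**Step 2. Add the early rule.** Excessive toxicity is declared if X20 ≥ 4, or if X20 ≤ 3 and X20 + X25 ≥ 5:

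P(declare) = P(X20 ≥ 4) + Σ(k = 0 to 3) P(X20 = k) × P(X25 ≥ 5 − k)

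| True rate | Early stop, P(X20 ≥ 4) | Reach 45 with ≥ 5 events | Sum | Stated |
|---|---|---|---|---|
| 5% | 0.0159 | 0.0607 | 0.0766 | 7.3% |
| 15% | 0.3523 | 0.4760 | 0.8283 | 82.5% |

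**Step 3. Check by the difference.** The two calculations disagree only when exactly 4 of the first 20 and none of the next 25 have an event. With 5 or more in the first 20, the fixed-sample rule is already met. The added probability is therefore P(X20 = 4) × (1 − p)^25, with P(X20 = 4) = 4845 × p^4 × (1 − p)^16:

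- p = 0.05: 0.01333 × 0.27739 = 0.0037, and 0.0729 + 0.0037 = 0.0766.
- p = 0.15: 0.18212 × 0.01720 = 0.0031, and 0.8252 + 0.0031 = 0.8283.

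Both routes agree. The shifts are 0.37 and 0.31 percentage points.

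**The case against.** The strongest reply is that nothing has been miscalculated. Both stated figures reproduce, the Précis openly describes a single-stage design with an early stopping rule, and 10.3.1 justifies that rule separately. The opening clause of the 10.2 sentence can fairly be read as fixing n = 45 for the calculation rather than as claiming to cover the stop. The early rule is almost contained in the final one, so adding it barely moves the numbers. There is also little left to act on: section 1.2.10 reports no grade 3 or higher neuropathy among the first 20 patients (a narrower event than neurologic toxicity), and section 13.1.1 speaks of active recruitment and treatment in the past tense.

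Most of this stands, and it limits the size of the point. It does not cover the wording, which states something the calculation does not show. Nor does it supply the joint figures, which appear nowhere.

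Three stronger readings are tempting and are not supported.

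- *That 82.5% overstates detection by 9 points.* Among trials that do not stop early, the chance of 5 or more events in 45 at a true 15% is 0.4760 / (1 − 0.3523) = 73.5%. That is not the design's detection probability. It leaves out the 35.2% of trials that stop early, which 10.3.1 counts as findings of excessive toxicity. On the whole design the stated figure is slightly too low.
- *That the stated figures do not describe this design at all.* They are within 0.4 points of the values that do.
- *That the early stop makes the rule unreliable at the 10% limit.* The probability of declaring excess there is 47.9% with the stop and 47.3% without it, so it comes almost entirely from the cutoff of 5 in 45, which is a separate matter.

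**Conclusion.** Wrong as written, minor. The arithmetic in 10.2 is right for a fixed sample of 45. The sentence misdescribes it as the probability of the true rate, and it leaves out a rule that leads to the same conclusion. For the design as planned, the probability of declaring excessive toxicity is 7.7% at a true rate of 5% (stated 7.3%, slightly understated) and 82.8% at 15% (stated 82.5%). The sample size, both thresholds and any decision taken under them are unaffected.

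This rests on four assumptions: independent outcomes with a common rate; the early rule applied to the first 20 evaluable patients, scored over the same two cycles; an early stop counted as a finding of excessive toxicity, as 10.3.1 says; and no use made of patients already enrolled but not yet scored when the fourth event is confirmed.

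**What to change.** Replace the probability sentence in section 10.2 with:

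> Including the early stopping rule, the probability of declaring excessive toxicity is 7.7% if the true rate is 5% and 82.8% if it is 15%.

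This one edit supplies the joint figures and puts the conditional the right way round. Leave the 5-in-45 cutoff, the 4-in-20 stop and the sample size as they are. The cost is two figures and a clause, and a false-alarm probability 0.4 points less favourable than the one now printed. If the protocol is not amended again, the same sentence can go into the statistical methods of the final report.
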